Therefore, the vaccine regimen in the SUIV groups will consist of sequential primary intramuscular immunization with one dose (Day 1) or 2 doses (Day 1 and Day 57) followed by a booster dose at Month 14 of a vaccine containing split inactivated influenza virus expressing a chimeric HA with at each dose the same stalk domain (H1 stalk) but a different exotic head. The SUIV vaccine will be adjuvanted with AS03_A or AS01_E or non-adjuvanted. The interval of two months between the two priming doses was selected to ensure optimal priming in a setting where the vaccine can be administered the whole year round without time pressure for completion of vaccination in contrast with a seasonal or pandemic influenza vaccination setting. The booster dose at Month 14 is anticipated to be necessary to obtain an adequate and persisting anti-stalk antibody response. In the control group, subjects will be administered one dose of *Fluarix Quadrivalent* inactivated influenza vaccine (IIV4) on Day 1 and then re-vaccinated at Month 14 with the next year’s formulation.

The main purpose of this study will be to assess the safety and the reactogenicity of each SUIV compared to IIV4. This study will also evaluate the adjuvant effect of AS03_A and AS01_E on the immune response when compared to the non-adjuvanted formulation. In addition, the immune response after 1 priming dose and after 2 priming doses will be evaluated, as well as the immune response after a booster dose given 14 or 12 months after a one dose priming schedule or a 2-dose priming schedule, respectively. Since the vaccine sequence of the priming dose and the booster dose in the one dose-priming schedule groups varies, the effect of the chimeric HA vaccine sequence on the humoral immune response will also be assessed. Finally, the cell-mediated immune response and the protective effect *in vivo* of the anti-stalk antibodies will be explored. Passive surveillance will be put in place in order to capture the occurrence of *influenza-like illnesses* during the entire study period. (Amended: 11 July 2019)

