2. OBJECTIVES

2.1. Primary objectives

- To assess the reactogenicity and safety of each vaccine dose throughout the entire study period, in all study groups.
- To describe the anti-H1 stalk humoral immune response 28 days after each priming dose (1 or 2 dose(s)) in all study groups.

Refer to Section [10.1](#) for the definition of the primary endpoints.

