3. STUDY DESIGN OVERVIEW

Figure 1 Study design overview

*If a subject presents signs and symptoms of influenza-like illness (ILI) (see Section 5.4.2), nasal and throat swabs will be collected as soon as possible (preferably within 24 hours, but not later than 7 days) after the onset of an ILI to test for influenza and/or other respiratory pathogens by RT-PCR if deemed necessary or for storage. (Amended: 11 July 2019)

**IDMC reviews will be performed throughout the study (refer to Section 8.8).

Protocol waivers or exemptions are not allowed unless necessary for the management of immediate safety concerns. Therefore, adherence to the study design requirements, including those specified in the outline of study procedures (Section 5.5), are essential and required for study conduct.

- **Experimental design:** Phase I/II, observer-blind, randomized, controlled, multi-centric study with 10 parallel groups.
- **Duration of the study:**
 - Epoch 001: Screening (Day -28 to -2) – only for Phase I subjects (refer to the [Enrolment](#) section).
 - Epoch 002: Primary starting at Visit 1 (Day 1) and ending at Visit 7 (Month 8).
 - Epoch 003: Booster starting at Visit 8 (Month 14) and ending at Visit 12 (Month 26).
- **Primary Completion Date (PCD):** Visit 12 (Month 26).
Refer to [glossary of terms](#) for the definition of PCD.
- **End of Study (EoS):** Last testing results released of samples collected at Visit 12 (Month 26).
Refer to [glossary of terms](#) for the definition of EoS.
- **Study groups:**
 - **cH8/P/cH5-AS03 group:** subjects receiving one dose of cH8/1N1+AS03 at Day 1, one dose of PBS at Day 57 and one booster dose of cH5/1N1+AS03 at Month 14.
 - **cH5/P/cH8-AS03 group:** subjects receiving one dose of cH5/1N1+AS03 at Day 1, one dose of PBS at Day 57 and one booster dose of cH8/1N1+AS03 at Month 14.
 - **cH8/5/11-AS03 group:** subjects receiving one dose of cH8/1N1+AS03 at Day 1, one dose cH5/1N1+AS03 at Day 57 and one booster dose of cH11/1N1+AS03 at Month 14.
 - **cH8/P/cH5-AS01 group:** subjects receiving one dose of cH8/1N1+AS01 at Day 1, one dose of PBS at Day 57 and one booster dose of cH5/1N1+AS01 at Month 14.
 - **cH5/P/cH8-AS01 group:** subjects receiving one dose of cH5/1N1+AS01 at Day 1, one dose of PBS at Day 57 and one booster dose of cH8/1N1+AS01 at Month 14.
 - **cH8/5/11-AS01 group:** subjects receiving one dose of cH8/1N1+AS01 at Day 1, one dose cH5/1N1+AS01 at Day 57 and one booster dose of cH11/1N1+AS01 at Month 14.

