4. STUDY COHORT

4.1. Number of subjects/centers

This study will be conducted in multiple centers. A total of 470 subjects (47/group) are planned to be enrolled in this study, in order to have 430 evaluable subjects for the primary immunogenicity endpoints. Refer to Section 10.4 for a detailed description of the criteria used in the determination of sample size.

Table 4 Sub-cohort (Amended: 11 July 2019)

Sub-cohort name	Description	Estimated number of subjects
Cell-mediated immunity (CMI) testing	Additional blood sample (~40 mL) to be taken at Visits 1, 2, 3, 5, 6, 8, 9 and 10 for CMI testing. This will be done at pre-specified sites with adequate material for such sampling procedure.	Approximately 225 The sub-cohort will consist of the first Phase II subjects enrolled in pre-specified sites.

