5.2.2.2.1. Study group and treatment number allocation

The target will be to enroll ~470 eligible subjects who will be randomly assigned to 10 study groups in a (1:1:1:1:1:1:1:1:1:1) ratio (~47 subjects in each group).

Allocation of the subject to a study group at the investigator site will be performed using SBIR. The randomization algorithm will use a minimization procedure accounting for center, sex, age (18-30 years vs. 31-39 years) and history of influenza vaccination since the 2014/2015 season (yes vs. no). Minimization factors will have equal weight in the minimization algorithm.

After obtaining the signed and dated ICF from the subject and having checked the eligibility of the subject, the site staff in charge of the vaccine/product administration will access SBIR. Upon providing the subject identification number, the randomization system will determine the study group and will provide the treatment number to be used for the first dose.

The number of each administered treatment must be recorded in the eCRF on the Vaccine Administration screen.

When SBIR is not available, please refer to the SBIR user guide or the SPM for specific instructions.

5.2.2.2. *Treatment number allocation for subsequent doses*

For each dose subsequent to the first dose, the study staff in charge of the vaccine/product administration will access SBIR, provide the subject identification number, and the system will provide a treatment number consistent with the allocated study group.

The number of each administered treatment must be recorded in the eCRF on the Vaccine Administration screen.

5.3. *Method of blinding*

Data will be collected in an observer-blind manner. By observer-blind, it is meant that during the course of the study, the vaccines/products recipient and those responsible for the evaluation of any study endpoint (e.g. safety, reactogenicity) will all be unaware of which vaccine/product was administered. To do so, vaccine/product preparation and administration will be done by authorized medical personnel who will not participate in any of the study clinical evaluation assays.

The site staff will work in an observer-blind manner during the entire study. As the vaccines appearance and preparation are different, two teams of study personnel will be set up:

- A team of unblinded personnel (responsible for the reception, preparation and administration of the vaccines).

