10. STATISTICAL METHODS

10.1. Primary endpoints

Reactogenicity and safety

- Occurrence of solicited local and general AEs after each vaccination:
 - Occurrence of solicited local AEs during a 7-day follow-up period (i.e. on the day of vaccination and 6 subsequent days) after each vaccine dose, in all vaccine groups.
 - Occurrence of solicited general AEs during a 7-day follow-up period (i.e. on the day of vaccination and 6 subsequent days) after each vaccine dose, in all vaccine groups.
- Occurrence of unsolicited AEs after each vaccination:
 - Occurrence of unsolicited AEs during a 28-day follow-up period (i.e. on the day of vaccination and 27 subsequent days) after each vaccine dose, in all vaccine groups.
- Occurrence of hematological and biochemical laboratory abnormalities after each vaccination:
 - Any hematological (red blood cells, white blood cells and differential count, platelets count and hemoglobin level) or biochemical (alanine aminotransferase, aspartate aminotransferase, creatinine, blood urea nitrogen [BUN] and BUN-to-creatinine ratio) laboratory abnormality at each visit subsequent to Day 1, in all vaccine groups.
- Occurrence of MAEs, pIMDs and SAEs:
 - Occurrence of MAEs, pIMDs and SAEs throughout the entire study period, in all vaccine groups.

Immunogenicity

Anti-H1 stalk immune response measured by ELISA and by MN assay 28 days after each priming dose:

- Levels of anti-H1 stalk antibody titers by ELISA and by MN assay.

The following aggregate variables will be calculated for the above parameters with 95% confidence interval (CI):

- Seropositivity rates and geometric mean titers (GMTs) at Days 1, 29 and 85.

- Percentage of subjects with a \geq 4-fold increase from Day 1 to Days 29 and 85.
- Percentage of subjects with a \geq 10-fold increase from Day 1 to Days 29 and 85.
- Mean geometric increase (MGI) from Day 1 to Days 29 and 85.

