10.8. Analysis of safety

The analysis will be performed on the ES.

All analyses will be descriptive. Data will be presented by dose, overall/dose and overall/subject. Outputs will be presented by study group. Analyses will be repeated pooling groups according to the adjuvant (AS01, AS03, no adjuvant).

- The percentage of subjects with at least one local AE (solicited and unsolicited), with at least one general AE (solicited and unsolicited) and with any AE during the solicited follow-up period will be tabulated with exact 95% CI. The same calculations will be performed for AEs rated as grade 3.
- The percentage of subjects reporting each individual solicited local and general AE during the solicited follow-up period will be tabulated with exact 95% CI. The same tabulation will be performed for grade 3 AEs and for AEs with relationship to vaccination.
- The verbatim reports of unsolicited AEs will be reviewed by a physician and the signs and AEs will be coded according to the Medical Dictionary for Regulatory Activities (MedDRA). The percentage of subjects with at least one report of unsolicited AE classified by the MedDRA and reported up to 28 days after vaccination will be tabulated with exact 95% CI. The same tabulation will be performed for grade 3 unsolicited AEs and for unsolicited AEs with a relationship to vaccination.
- The percentage of subjects with MAE(s) will be summarized by group with exact 95% CI.
- The percentage of subjects with episode(s) of ILI will be summarized by group with exact 95% CI. **(Amended: 11 July 2019)**
- At each hematology/biochemistry sampling timepoint, by study group, individual hematological and biochemical values will be presented as number of subjects out of range (above and below normal range) and tabulated by toxicity grading (refer to [APPENDIX C](#)). In addition, changes from baseline (median/interquartile range) will be presented.
- SAEs and pIMDs will be described in detail. Withdrawals due to (S)AEs will also be summarized.

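### Section 10.8 summarises Dose 1 safety by study group and by adjuvant, but not by vaccine given, so each cH8/1N1 formulation gets no pooled estimate on its roughly 94 recipients

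*Protocol*

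**What the plan says.** Section 1.2.2 states the aim at vaccine level: "The main purpose of this study will be to assess the safety and the reactogenicity of each SUIV compared to IIV4". Section 2.1 words the primary safety objective by dose and group: "To assess the reactogenicity and safety of each vaccine dose throughout the entire study period, in all study groups". Section 10.1 follows it, with solicited events counted over seven days, "i.e. on the day of vaccination and 6 subsequent days) after each vaccine dose, in all vaccine groups".

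The level of reporting is set in section 10.8, not in 10.1. Section 10.8 says "Data will be presented by dose, overall/dose and overall/subject", and then: "Outputs will be presented by study group. Analyses will be repeated pooling groups according to the adjuvant (AS01, AS03, no adjuvant"). The split by dose operates within those two levels. No summary by vaccine administered is named.

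Section 3 and Table 17 in section 6.3 show what each group receives. Taking AS03 as the example, cH8/P/cH5-AS03 receives cH8/1N1+AS03 on Day 1 and PBS on Day 57. The cH8/5/11-AS03 group is described as "subjects receiving one dose of cH8/1N1+AS03 at Day 1, one dose cH5/1N1+AS03 at Day 57". The first dose is the same. The same pairing holds for AS01 and for the non-adjuvanted groups. The third group in each adjuvant stratum, cH5/P/cH8-X, starts with cH5/1N1.

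**The concern.** Six SUIV formulations are given at Dose 1: cH8/1N1 and cH5/1N1, each with AS03, with AS01 or without adjuvant. For the three cH8/1N1 formulations, two randomised groups are treated alike until Dose 2. Neither planned level of reporting uses that to estimate the vaccine's own Dose 1 event rate:

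- By study group, one product appears in two columns of about 47, each with an interval sized for 47.
- By adjuvant, the column holds about 141 subjects, two thirds given cH8/1N1 and one third given cH5/1N1. It estimates the cH8/1N1 rate only if the two antigens have the same rate.

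What is at stake is the precision of a primary, descriptive safety result in an early-phase study. There is also a smaller presentational risk. Section 10.10 says comparative analyses aim to characterise differences between groups, yet a Dose 1 difference between cH8/P/cH5-X and cH8/5/11-X can only be chance.

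**Working it through.** **Inputs.** Section 4.1: "A total of 470 subjects (47/group) are planned to be enrolled in this study". Section 5.2.2.2.1: subjects "who will be randomly assigned to 10 study groups" in equal ratio. Section 10.8: exact 95% confidence intervals for event percentages. Table 7: Visit 4 (Dose 2) falls 56 to 66 days after Visit 1.

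**Reproducing the plan's own figures (section 10.4.1, 45 per group).**
- Zero-event upper limit: 1 − 0.025^(1/45) = 0.0787. Table 26 states 0.079.
- 10 of 45 events: exact interval 0.112 to 0.371, as in Table 26.
- True rate giving at least one event with 90% probability: 1 − 0.1^(1/45) = 0.0499. Table 25 states 0.049, which looks truncated rather than rounded.

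The method is the plan's own; only n changes below.

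**Is pooling legitimate?** The two groups are randomised, receive the same first injection and differ only from Dose 2. The 7-day and 28-day windows close before the earliest scheduled Dose 2 at 56 days. The Visit 2 and Visit 3 blood samples also precede it, and the Visit 4 sample is taken before vaccine administration (footnote to Tables 5 and 6). Pooling therefore needs no modelling assumption.

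**Numbers per cH8/1N1 formulation at Dose 1.** 2 × 47 = 94. The adjuvant pool is 94 + 47 = 141.

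| Quantity | Formula | n = 47 | n = 94 |
|---|---|---|---|
| Upper exact 95% limit, no events | 1 − 0.025^(1/n) | 7.5% | 3.8% |
| True rate seen at least once with 90% probability | 1 − 0.1^(1/n) | 4.8% | 2.4% |
| Probability of at least one event at a true 2% rate | 1 − 0.98^n | 61% | 85% |
| Exact 95% interval at 10.6% observed (5/47, 10/94) | beta quantiles | 3.5% to 23.1% | 5.2% to 18.7% |

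On the plan's basis of 45 per group (45 to 90), the first two rows become 7.9% to 4.0% and 5.0% to 2.5%.

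**What the adjuvant pool estimates.** (94 × p8 + 47 × p5) / 141, where p8 and p5 are the cH8/1N1 and cH5/1N1 rates. With illustrative rates of 10% and 20%: (9.4 + 9.4) / 141 = 13.3%, which is neither antigen's rate.

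**Chance differences between identical columns.** Take an assumed true rate of 20% and two independent groups of 47. They differ by 5 or more subjects (5/47 = 10.6 points) with probability 0.24. At least one of the three pairs does so with probability 1 − (1 − 0.2445)³ = 0.57. At an assumed 10% rate the figures are 0.12 and 0.32.

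**The case against.** The strongest reply is that nothing here is wrong. The objective says all study groups, the endpoint says all vaccine groups, the precision tables are built on one group, and holding rules 2a to 2c also work by group. By-group tables satisfy all of these. The sentence about each SUIV is a rationale and sets no pooling rule. Safety is wholly descriptive, so no decision turns on the width of a Dose 1 interval. Pooling by adjuvant is a reasoned choice: the antigens share stalk, neuraminidase and HA content, the listed theoretical autoimmune risk relates to adjuvants, and 141 subjects give a zero-event limit of 2.6%. Extra columns in safety tables are often left to the statistical analysis plan.

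Most of this stands, and it limits the point to an improvement. Two parts do not dispose of it. First, the protocol did choose to specify a pooling level, and the chosen level does not answer the vaccine-level purpose in section 1.2.2. The tighter limit of 2.6% applies to a mixture of two antigens. Second, a reader can add two columns to get a pooled count, but must then compute the exact interval separately. The median and interquartile range of laboratory changes cannot be recovered from two group summaries.

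A reader might infer that half of the cH8/1N1 data is discarded, or that the Dose 1 results are biased. The documents support neither: every recipient is tabulated, and each group column is an unbiased estimate for that vaccine. Nor can it be said that a pooled estimate will never be produced. Section 10.8 does not exclude further summaries, and the analysis plan is not at hand. The Exposed Set rule in section 10.5.1, to analyse by treatment actually administered, assigns subjects as treated and does not itself create a pool by vaccine.

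**Conclusion.** The point holds as a modest loss of precision. The safety tables stated in section 10.8 give no pooled Dose 1 estimate with exact interval for any of the three cH8/1N1 formulations, although about 94 subjects receive each one under identical, randomised conditions. Supplying it would roughly halve the zero-event upper limit (7.5% to 3.8%) and the rate seen at least once with 90% probability (4.8% to 2.4%).

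These figures assume 47 subjects per group as planned. Denominators for solicited events may be smaller, because section 10.6 counts only doses with a completed symptom screen. The validity of the existing tables is not in question, and the primary objective as worded is met. The presentational risk is minor, since the group definitions show that the first doses are the same.

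**What to change.** Add to section 10.8: For Dose 1, solicited AEs (7 days), unsolicited AEs (28 days) and laboratory results from visits before Dose 2 will also be summarised by vaccine administered, pooling cH8/P/cH5-X with cH8/5/11-X for each adjuvant level X, with the cH5/1N1 formulations and IIV4 alongside; events are counted up to each subject's Dose 2 administration.

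The boundary should be each subject's own Dose 2 rather than a fixed Day 57, because Table 7 lets Visit 4 fall 56 to 66 days after Visit 1. Blood drawn at Visit 4 before the injection then belongs to the Dose 1 period.

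Keep the by-group and by-adjuvant tables as they are. The cost is one extra set of descriptive tables from data already collected, with no change to conduct, sample size or blinding.

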10.2. Secondary endpoints (Amended: 11 July 2019)

Immunogenicity

Adjuvant effect on the anti-stalk immune response in terms of:

- GMT ratio for anti-stalk ELISA titer SUIV+AS03 or AS01/SUIV non-adjuvanted, 28 days post vaccination (i.e. at Day 29 to evaluate the adjuvant effect post-dose 1 and at Day 85 to evaluate the adjuvant effect post-dose 2).

Anti-H1 stalk immune response measured by ELISA and by MN assay:

- Levels of anti-H1 stalk antibody titers by ELISA post-each vaccination.

The following aggregate variables will be calculated for the above parameters with 95% CI:

- Seropositivity rates and GMTs at Days 1, 29, 85, Month 8, Month 14, Month 14 + 28 days, Month 20 and Month 26.
- Percentage of subjects with a \geq 4-fold increase in antibody titers by ELISA from Day 1 to each subsequent timepoint listed above.
- Percentage of subjects with a \geq 10-fold increase in antibody titers by ELISA from Day 1 to each subsequent timepoint listed above.
- MGI in antibody titers by ELISA from Day 1 to each subsequent timepoint listed above.
- Levels of anti-H1 stalk antibody titers by MN assay.

The following aggregate variables will be calculated for the above parameters with 95% CI:

- Seropositivity rates and GMTs at Days 1, 29 **and** 85.
- Percentage of subjects with a \geq 4-fold increase in antibody titers by MN assay from Day 1 to each subsequent timepoint listed above.
- Percentage of subjects with a \geq 10-fold increase in antibody titers by MN assay from Day 1 to each subsequent timepoint listed above.
- MGI in antibody titers by MN assay from Day 1 to each subsequent timepoint listed above.

Breadth of the immune response:

- Levels of anti-H2 and anti-H18 antibody titers by ELISA.

The following aggregate variables will be calculated for the above parameters with 95% CI:

- Anti-H2 and anti-H18 seropositivity rates and GMTs at Days 1, 29, 85, Month 8, Month 14, Month 14 + 28 days, Month 20 and Month 26.
- Percentage of subjects with a \geq 4-fold increase in anti-H2 and anti-H18 antibody titers from Day 1 to each subsequent timepoint listed above.
- Percentage of subjects with a \geq 10-fold increase in anti-H2 and anti-H18 antibody titers from Day 1 to each subsequent timepoint listed above.
- MGI in anti-H2 and anti-H18 antibody titers from Day 1 to each subsequent timepoint listed above.
- Levels of antibody titers by MN assay for H1N1 swine influenza and IIV4 H1N1 vaccine strains.

The following aggregate variables will be calculated for the above parameters with 95% CI:

- Seropositivity rates and GMTs at Days 1, 29 **and** 85.
- Percentage of subjects with a \geq 4-fold increase in antibody titers from Day 1 to each subsequent timepoint listed above.
- Percentage of subjects with a \geq 10-fold increase in antibody titers from Day 1 to each subsequent timepoint listed above.
- MGI in antibody titers from Day 1 to each subsequent timepoint listed above.

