2.2. Secondary objectives

- To evaluate the adjuvant effect of AS03 and AS01 on the humoral immune response after 1 and 2 priming dose(s) of investigational SUIVs when compared to the non-adjuvanted formulations.
- To describe the persistence of the anti-H1 stalk humoral immune response after each priming dose (1 or 2 dose(s)) in all study groups up to Month 14.
- To describe the humoral immune response after a booster dose at Month 14.
- To describe the breadth of the humoral immune response after each vaccination in all study groups.
- To describe the effect of the chimeric HA vaccination-sequence on the humoral immune response.

Refer to Section [10.2](#) for the definition of the secondary endpoints.

[figure not shown]

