10.6. Derived and transformed data

- The cut-off value is defined by the laboratory before the analysis and is described in Section 5.7.3. A seronegative subject is a subject whose titre is below the cut-off value. A seropositive subject is a subject whose titre is greater than or equal to the cut-off value.
- The GMTs calculations are performed by taking the anti-log of the mean of the log titre transformations. Antibody titres below the cut-off of the assay will be given an arbitrary value of half the cut-off for the purpose of GMT calculation.
- The MGI is defined as the geometric mean of the fold increase in serum HI titres post-vaccination compared to Day 1.
- All CIs are 95% CIs. The 95% CIs for GMT are obtained within each group separately. The 95% CI for the mean of log-transformed titre is first obtained assuming that log-transformed titres are normally distributed with unknown variance. The 95% CI for the GMT is then obtained by exponential-transformation of the 95% CI for the mean of log-transformed titre.
- Handling of missing data: for a given subject and a given immunogenicity measurement, missing or non-evaluable measurements will not be replaced. Therefore, analysis will exclude subjects with missing or non-evaluable measurements.
- Reactogenicity and safety
 - For the analysis of solicited symptom, missing or non-evaluable measurements will not be replaced. Therefore the analysis of the solicited symptoms based on the ES will include only subjects/doses with documented safety data (i.e. symptom screen completed).
 - For the analysis of unsolicited AEs/MAEs/ILIs/SAEs/concomitant medication, all vaccinated subjects will be considered and subjects who did not report an event will be considered as subjects without an event.

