10.9.1. Within group assessment

10.9.1.1. Humoral immunogenicity assessment

For each study group, at each timepoint at which the tests are done and results are available, for each humoral immunity parameter, the following analyses will be performed:

- Seropositivity rates and GMTs, with exact 95% CI.
- MGI from Day 1, with 95% CI.
- Percentage of subjects with at least 4-fold increase from Day 1, with exact 95% CI.
- Percentage of subjects with at least 10-fold increase from Day 1, with exact 95% CI.
- Distribution of antibody titers using reverse cumulative distribution curves.

The correlation between anti-H1 HA stalk ELISA and anti-H1 HA stalk MN assay results will be explored.

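### No fold-increase measure isolates the Month 14 booster: after the booster, every MGI and responder rate is still taken from Day 1

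*Protocol*

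**What the plan says.** Section 2.2 lists two separate secondary objectives that bear on this point. One is "To describe the humoral immune response after a booster dose at Month 14". The other begins "To describe the persistence of the anti-H1 stalk humoral immune response after each priming dose" and runs up to Month 14.

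Section 10.2 lists the anti-H1 stalk ELISA timepoints as Days 1, 29 and 85, Month 8, Month 14, Month 14 + 28 days, Month 20 and Month 26. GMTs and seropositivity rates with 95% CI are planned at each. The fold measures are "MGI in antibody titers by ELISA from Day 1 to each subsequent timepoint listed above" and the percentages with at least a 4-fold or 10-fold "increase in antibody titers by ELISA from Day 1 to each subsequent timepoint listed above". For breadth the rule is the same: "MGI in anti-H2 and anti-H18 antibody titers from Day 1 to each subsequent timepoint listed above".

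The within-group analysis in section 10.9.1.1 repeats the anchor: "MGI from Day 1, with 95% CI" and "Percentage of subjects with at least 4-fold increase from Day 1, with exact 95% CI", with a matching line for 10-fold. Neither section names a fold measure from Month 14.

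The footnotes to Tables 5 and 6 require blood to be drawn before vaccination, so the Visit 8 sample is pre-booster. Table 13 has it tested by all three ELISAs in about 470 subjects.

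Section 10.9.2.1 models 28-day post-booster log10 titers with the pre-vaccination titer as covariate and does not say which visit that is.

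**The concern.** Day 1 lies before one or two active priming doses in the SUIV groups. By Table 7 it also lies at least 56 + 336 = 392 days before the booster. A rise from Day 1 to Month 14 + 28 days therefore cannot be assigned to the booster.

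Two hypothetical subjects show this. One has 100 EU/mL on Day 1, 400 at Month 14 and 400 at Month 14 + 28 days. The other has 100, 100 and 400. Both count as 4-fold responders at Month 14 + 28 days, but only the second rose after the booster.

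Group comparisons can be affected too. Section 10.9.2.2 plans differences in the percentage with a fold increase from baseline, generally four weeks after a dose, and its contrasts include two priming doses against one. Those arms differ by design in the number of priming doses and in the interval to the booster (12 against 14 months, section 1.2.2). Their Month 14 titers may differ. A post-booster difference in Day 1 responder rates could then reflect persistence alone.

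**Working it through.** The protocol states no power or precision figure for the booster objective, so there is no figure to reproduce.

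**1. Decomposition.** For each subject:

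fold(Day 1 to Month 14 + 28 d) = fold(Day 1 to Month 14) × fold(Month 14 to Month 14 + 28 d)

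Taking geometric means in the same subjects: MGI from Day 1 = persistence fold P × booster fold B.

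**2. A booster with no effect (B = 1).** The share with at least a 4-fold rise is 1 − Φ((log10 4 − log10 F)/SD). F is the geometric mean fold from the chosen anchor and SD is that of the within-subject log10 change. The protocol gives neither P nor this SD; both are assumed. Section 10.4.1 uses an SD of 0.45 for log10 titers. From SD of change = 0.45 × √(2(1 − r)), a change SD of 0.45 corresponds to a within-subject correlation r of 0.5, and 0.30 to r of about 0.78. For simplicity the same SD is used for both anchors.

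| P at Month 14 | MGI from Day 1 | ≥4-fold from Day 1, SD 0.30 | SD 0.45 |
|---|---|---|---|
| 1.0 | 1.0 | 2.2% | 9.0% |
| 1.5 | 1.5 | 7.8% | 17.2% |
| 2 | 2.0 | 15.8% | 25.2% |
| 3 | 3.0 | 33.9% | 39.1% |

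Example: P = 2, SD 0.30 gives z = (0.602 − 0.301)/0.30 = 1.00, upper tail 0.158.

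From Month 14, F = B = 1 in every row, so the MGI is 1.0 and the share is 2.2% (SD 0.30) or 9.0% (SD 0.45). With P = 1 the two anchors agree.

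**3. What the planned outputs recover.** In the same subjects, GMT(Month 14 + 28 d)/GMT(Month 14) equals the MGI from Month 14 exactly. Three limits remain.

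- The subjects need not be the same. Section 10.5.2 adapts the Per-Protocol set by timepoint, and section 10.6 does not replace missing titers.
- The CI is not recoverable. GMT intervals are per timepoint, whereas the interval for the ratio depends on r. With n = 43 and SD 0.45, its 95% limits are the estimate divided and multiplied by 10^(t × 0.45 × √(2(1 − r))/√43), t on 42 degrees of freedom. The factor is 1.57 at r = 0, 1.38 at r = 0.5 and 1.22 at r = 0.8.
- A booster responder rate cannot be derived from two GMTs, nor from two Day 1 responder rates.

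**4. The ANCOVA covariate.** Tables 5, 6 and 13 label the Day 1 sample PRE, expanded as pre-vaccination, and label the Visit 8 sample M14. That points to Day 1, but section 10.9.2.1 does not settle it. A model of post-booster titer adjusted for Day 1 answers a different question from one adjusted for Month 14.

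**The case against.** A reader might infer that the booster objective goes unanswered. The protocol does not support that. The objective is only to describe, with no hypothesis or threshold. GMTs with CIs are planned immediately before and 28 days after the booster, and reverse cumulative curves at each tested timepoint. The Day 1 fold measures are also reported at Month 14 itself. In the null example with P = 2, the tables would show an MGI of 2 at both Month 14 and Month 14 + 28 days, so an attentive reader would see that nothing changed.

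A reader might also infer that persisting antibody is reported as booster response, or that the Month 14 titer is never used as a baseline. The first does not follow, since each measure is labelled as running from Day 1 and none is called a booster response. The second is not established, because the ANCOVA covariate is ambiguous.

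The general definition in section 10.6, "The MGI is defined as the geometric mean of the fold increase in serum HI titres post-vaccination compared to Day 1", adds little. It is worded for HI, which now stops at Day 85, so the point rests on sections 10.2 and 10.9.1.1.

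The Day 1 anchor is legitimate for cumulative response and is needed for the persistence objective. A Month 14 anchor can mislead in the other direction: a group with higher pre-booster titers may show a smaller fold rise yet reach the highest final titer. This is why both should be reported.

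Finally, a SAP may add Month 14-anchored summaries, and section 10.9.2.2 allows further ratios. That is possible, but the protocol itself fixes the reference time of these endpoints, so this is more than a detail left open. The sponsor's decision not to pursue development lowers the stakes. It does not change what the booster tables will mean.

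**Conclusion.** The point holds in a limited form. Every fold-increase measure planned after the booster combines persistence with booster rise, and none isolates the booster. A reader can approximate the booster rise from the planned tables, but cannot obtain a paired within-subject rise with its CI or a booster responder rate.

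The multiplication is exact; its size here is not known. The persistence folds and the SDs of change are assumptions, and if titers are back at Day 1 levels by Month 14 the problem disappears. No decision rule depends on it: the adjuvant criterion in section 10.4.2 uses Day 29 and Day 85, and the other between-group comparisons are descriptive. It is a free improvement to how the booster is described.

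**What to change.** In sections 10.2 and 10.9.1.1, add for the anti-H1 stalk, anti-H2 and anti-H18 ELISAs the MGI and the percentages with at least a 4-fold and a 10-fold increase from the pre-booster Month 14 (Visit 8) titer to Month 14 + 28 days, with 95% CI. Month 20 and Month 26 can be added if wanted.

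Keep the Day 1-anchored values, labelled as cumulative response. Report both sets beside the GMTs when describing the booster.

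In section 10.9.2.1, state whether the covariate in the post-booster ANCOVA is the Day 1 or the Month 14 titer.

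The cost is a few table rows and one clarifying sentence. The titers are already planned for all subjects, so no new samples, assays or subjects are needed.
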